6.1.8.4 Management of Decreased Spermatogenesis

Based on findings in a preclinical study of venetoclax, there is a potential for decreased spermatogenesis. Male subjects should consider sperm banking before treatment with venetoclax if they are considering preservation of fertility.

6.1.8.5 Management of Other Toxicities

If other events occur that are related to venetoclax or LDC the investigator, in consultation with the AbbVie medical monitor, may interrupt or dose reduce venetoclax and/or reference therapy, as appropriate. Grade 3 or greater nonhematologic toxicity (e.g., nausea, vomiting, and diarrhea when additional supportive care fails), that is related to venetoclax or LDC will require interruption and possible discontinuation of dosing. Venetoclax or LDC may be reintroduced, but only at a reduced dose, (in consultation with the AbbVie medical monitor) if the toxicity returns to \leq Grade 1 or to baseline if Grade 2 at study entry.

Subjects should be monitored for new onset hematologic toxicity and renal toxicities, with dose delay or reduction as appropriate. Please follow local, approved product label or applicable SmPC for monitoring guidelines.

6.1.8.6 Determination of the MTD

If a single subject within a cohort experiences a DLT, a total of 6 subjects will be enrolled and dosed at the same dose level. If these additional subjects do not exhibit a DLT, dose escalation may proceed. If any of the additional subjects exhibits a DLT, then dose de-escalation may occur to interrogate lower dose levels. The MTD, if identified, will be defined at the highest dose level at which less than 2 of 6 subjects or < 33% of (if cohort is expanded beyond 6) subjects experience a DLT.

6.1.8.7 Determination of the RPTD

If an MTD is reached, the RPTD will not be a dose higher than the MTD and will be selected by the sponsor based on the types of DLTs which occur and the MTD identified. If an MTD is not reached, then the RPTD will be defined based on the safety and PK data.

8.0 Statistical Methods and Determination of Sample Size

8.1 Statistical and Analysis Plans

Analysis will be performed separately for each phase of the study.

Efficacy and safety analyses will be performed on all subjects who receive at least one dose of venetoclax.

8.1.1 Baseline Characteristics

All baseline summary statistics and analyses will be based on characteristics obtained prior to the initiation of study drug. Unless otherwise stated, baseline for a given variable will be defined as the last value for that variable obtained prior to the first dose of study drug.

8.1.1.1 Demographics

Age, height, weight and gender will be summarized with means, standard deviation and range. Frequencies and percentages will be computed for the following parameters: race, smoking history, and performance status.

8.1.1.2 Medical History

Frequencies and percentages will be computed for each medical history parameter.

8.1.2 Pharmacokinetics

8.1.2.1 Tabulations and Summary Statistics

Plasma concentrations and PK parameter values of venetoclax and cytarabine will be tabulated for each subject, visit, and dose regimen, and summary statistics will be computed for each sampling time and each parameter.

8.1.2.2 Model and Tests

All analyses will be performed on the Phase 1 portion subjects only.

Dose Proportionality and Covariate Selection of Venetoclax

The following analysis will be performed separately on Cycle 1 Day 10 and Cycle 1 Day 18 venetoclax PK parameters.

An analysis will be performed for dose-normalized C_{max} , AUC_{24} , and other PK parameters provided that they can be adequately determined from the data. The model used for the statistical analyses will include designated cohort dose level. This may be done by

classifying subjects by dose level or, if appropriate, using dose level as a continuous variable. Covariates such as age, body weight, body surface area, gender, and perhaps others that might explain some of the variability in the population will be included in the model initially. However, a covariate may be dropped from the model if the regression coefficient is not significant at alpha level 0.10. The natural logarithmic transformation will be employed for C_{max} and the AUC's unless the data clearly indicate that other transformation or the untransformed variable provides more nearly symmetric probability distributions and/or more nearly homogenous variances across dose levels. Within the framework of the model, tests that have good power for a trend with dose will be performed on the effect of designated cohort dose level.

Venetoclax Effect on Cytarabine Pharmacokinetics Parameters

A linear mixed effects analysis will be performed for C_{max} , AUC_t and AUC_{∞} , to compare cytarabine PK parameters when co-administered with venetoclax (Cycle 1 Day 10) relative to cytarabine administered alone (Cycle 1 Day 1). For C_{max} and AUC, the logarithmic transformation will be used unless the data indicate that the logarithm has significant non-normality. The model will include effects for visit (Cycle 1 Day 1, Cycle 1 Day 10). To account for the correlation among visits, the repeated statement for the visit effect will be specified under SAS procedure mixed. The relative bioavailability of cytarabine co-administered with venetoclax relative to cytarabine alone will be estimated and a 90% confidence interval will be provided for each of C_{max} and AUC. The confidence intervals will be obtained by the antilogarithm of the endpoints of confidence intervals for the difference of mean logarithms obtained within the mixed modeling framework.

Cytarabine Effect on Venetoclax Pharmacokinetics Parameters

A similar analysis to venetoclax effect on cytarabine PK parameters will be performed on Cycle 1 Day 10 and Cycle 1 Day 18 venetoclax PK parameters.

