Adverse event (AE) monitoring, vital signs, physical examination, electrocardiogram (ECG) and laboratory values will be assessed. Guidelines for Tumor Lysis Syndrome (TLS) management are provided. Note: All subjects will be hospitalized during dose ramp-up and longer as needed, per investigator judgment, for bone marrow recovery or for management of disease complications during the escalation from each subjects starting dose through at least 24 hours beyond each subject receiving their maximal venetoclax dose level. Chemistry labs pertinent to TLS (including potassium, calcium, uric acid, phosphorus, and creatinine) will be performed at pre-dose, 6, and 12 hours post-dose for the first dose and each escalated dose, and also as deemed necessary to monitor for TLS. Chemistries will also be performed at 24 hours after administration of the highest venetoclax dose level.

Statistical Methods:

Efficacy:

Analyses of ORR as defined by CR + CRi + PR, CR rate, CRi rate, CRh rate, CR + CRi rate, CR + CRh rate, duration of response (DOR), event free survival (EFS), overall survival (OS), the exploratory analysis of the proportion of all subjects who achieve minimal residual disease (MRD) negativity, the proportion of subjects who are transfusion independent post baseline, and the proportion of subjects who undergo subsequent stem cell transplant will be performed for subjects who received study drugs.

Pharmacokinetic:

Plasma concentrations and PK parameter values of venetoclax and cytarabine will be tabulated for each subject, visit, and dose regimen, and summary statistics will be computed for each sampling time and each parameter.

The dose proportionality of venetoclax and the potential interaction between venetoclax and cytarabine will be assessed using linear mixed effect model.

Safety:

A safety analysis will be performed for all dosed subjects unless otherwise indicated. For the study as a whole, adverse events will be evaluated and summarized. Laboratory test results and vital signs will be explored for trends and summarized as appropriate.

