5.0 Studies/Protocols

A complete list of relevant clinical studies associated with venetoclax that will be contributed to the product efficacy assessment is listed in [Table 1](#).

Table 1. Studies to be Included in Efficacy Summary

Study ID Phase (Status)	Number of Enrolled Subjects (Actual/Planned)	Location	Study Design	Primary Objective
M14-358 Phase 1b (Enrollment complete and follow-up is ongoing)	212/260	Australia, Germany, France, and US	Open-label study of venetoclax + azacitidine or decitabine in treatment naïve elderly (≥ 60 years) subjects with AML who are not eligible for standard induction therapy; 2 stages: dose escalation and dose expansion (both HMAs)	Evaluate the safety, PK, and efficacy of venetoclax + decitabine or azacitidine in the target population. The objective of the safety expansion is to confirm efficacy and safety of the intended dose for Phase 3 study.
M14-387 Phase 1/2 (Enrollment complete and follow-up is ongoing)	92/92	Australia, Germany, Italy, US	Open-label study of venetoclax + LDAC in treatment naïve subjects with AML who are ≥ 60 years of age and who are not eligible for standard anthracycline-based induction therapy; 2 stages: dose escalation and safety expansion	Phase 1: Evaluate the safety, PK and determine the MTD and RPTD of venetoclax + LDAC. Phase 2: Estimate efficacy, including ORR, and characterize the toxicity of the combination at the RPTD. Cohort C: Evaluate the ORR for subjects allowed additional supportive medications (strong CYP3A inhibitors) if medically indicated.

The venetoclax doses and regimens in the Studies listed in [Table 1](#) are described in [Table 2](#) below.

Table 2. Regimens Investigated in Venetoclax AML Studies

Study ID	Venetoclax Dose and Frequency	Treatment Regimen
M14-358	Venetoclax 400 mg QD, 800 mg QD, 1200 mg QD	Venetoclax in combination with HMA (Azacitidine or Decitabine)
M14-387	Venetoclax 600 mg QD, 800 mg QD	Venetoclax in combination with LDAC (Low dose cytarabine)

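### Venetoclax dose proportionality rests on a trend test with no estimate or interval; with only 600 and 800 mg given, a non-significant result is not evidence of proportionality

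*Protocol*

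**What the plan says.** The Protocol synopsis (1.2, Statistical Methods, Pharmacokinetic) announces the analysis: "The dose proportionality of venetoclax and the potential interaction between venetoclax and cytarabine will be assessed using linear mixed effect model". Section 8.1.2.2 gives the detail.

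- Population: "All analyses will be performed on the Phase 1 portion subjects only".
- Days: "The following analysis will be performed separately on Cycle 1 Day 10 and Cycle 1 Day 18 venetoclax PK parameters". Each test therefore uses one value per subject.
- Endpoint: "An analysis will be performed for dose-normalized" Cmax, AUC24 and other parameters, log-transformed by default. Dose level may enter as a class or as a continuous variable.
- Inference on dose: "tests that have good power for a trend with dose will be performed on the effect of designated cohort dose level".
- The only alpha in the subsection concerns covariates: "a covariate may be dropped from the model if the regression coefficient is not significant at alpha level 0.10". None is given for the dose test.

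The next subsection, on cytarabine exposure with and without venetoclax, plans an estimate of relative bioavailability, and "a 90% confidence interval will be provided for each of C"max and AUC. The dose-proportionality subsection has no counterpart to this.

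On doses, Protocol 5.6.4 lists target doses from 200 to 2000 mg. Table 2 of the efficacy SAP (section 5.0) gives what was used in this study: "Venetoclax 600 mg QD, 800 mg QD". Its Table 3 shows 92 treated subjects, 82 of them at 600 mg.

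**The concern.** Because exposure is dose-normalized, a significant dose effect is evidence against proportionality, while a non-significant one shows only that no departure was detected. A trend test is a sensible choice over many dose levels. With two levels, the class and continuous versions of dose reduce to the same one-degree-of-freedom contrast, so choosing a trend test adds no power. The two doses are also close together, and one has 10 subjects.

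Characterising PK is a Phase 1 primary objective. If the analysis returns only a p-value, a reader has no means of judging which departures from proportionality the data exclude.

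**Working it through.** The plan states no power, CV or alpha for this test, so it has no figure of its own to reproduce.

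**Inputs**
- Doses: 600 and 800 mg (efficacy SAP, Table 2). ln(800/600) = 0.288.
- 800 mg: 92 - 82 = 10 subjects (efficacy SAP, Table 3). All are taken as Phase 1, because Protocol 5.1 shows both Phase 2 parts at 600 mg.
- 600 mg in Phase 1: not stated. Assumed 6 (a full 3+3 cohort) to 12. The upper figure uses planned Phase 2 sizes: 92 - 50 - 20 = 22 in Phase 1, less 10. An extreme bound is 42 - 10 = 32, from the Phase 1 maximum.
- Between-subject CV: not stated. Shown from 20% to 60%.
- Alpha: not stated. Two-sided 0.05 assumed, with 0.10 as a variant.

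**Formulas**
- Log SD = sqrt(ln(1 + CV²)); SE of the log ratio = SD × sqrt(1/n1 + 1/n2).
- In a power model with exponent b, the difference in log dose-normalized exposure is (b - 1) × 0.288. Flat exposure (b = 0) gives a ratio of 600/800 = 0.75. Half-proportional exposure (b = 0.5) gives half that log difference.
- Power from the noncentral t with n1 + n2 - 2 degrees of freedom.

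Example, CV 50%, 12 v 10: SD = sqrt(ln 1.25) = 0.472; SE = 0.472 × sqrt(1/12 + 1/10) = 0.202; noncentrality = 0.288/0.202 = 1.42; power = 27%.

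**Power against flat exposure, two-sided 0.05**

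| CV | 6 v 10 | 8 v 10 | 12 v 10 | 32 v 10 |
|---|---|---|---|---|
| 20% | 74% | 82% | 90% | 98% |
| 25% | 56% | 64% | 74% | 88% |
| 30% | 42% | 49% | 59% | 75% |
| 40% | 27% | 32% | 38% | 52% |
| 50% | 20% | 23% | 27% | 38% |
| 60% | 16% | 18% | 21% | 29% |

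Power falls below 50% once the CV exceeds 27%, 30%, 34% and 41% respectively. At alpha 0.10 the first three thresholds become 33%, 36% and 41%; for example, 12 v 10 at CV 40% then has power 52%.

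**Half-proportional exposure.** At CV 20%, power is 26% (6 v 10) to 37% (12 v 10), and 50% at 32 v 10. At CV 40-60% with 12 v 10 it is 9-13%.

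**The range planned upward from the starting dose.** With five levels from 600 to 2000 mg and CV 50%, the slope test would have power of 92% (3 per level) or over 99% (6 per level) against flat exposure.

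**What an interval would show.** If the observed 800/600 dose-normalized ratio were 1.0, the 90% CI is exp(±t × SE). At CV 50% and 12 v 10, t (20 df, 0.95) = 1.725, which gives 0.71-1.42. This includes 0.75, so flat exposure is not excluded. At CV 30% it is 0.81-1.24, which excludes 0.75.

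**The case against.** The phrase about good power describes a class of test, trend rather than omnibus. A reader might infer that the protocol claims a power which the design lacks. It states none, and over the planned range the method would have performed well. Ending with two close levels was the result of escalation. This stands: the shortfall is that the text was not revised.

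A reader might also infer that a complete failure of exposure to rise would usually be missed. The documents do not support that without conditions, because CV, alpha and the Phase 1 number at 600 mg are all unstated. At CV 20-25% flat exposure is found more often than missed. Section 8.1.2.2 also starts with covariates that may reduce residual variance, so the CV above is best read as the residual one.

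The trend test is not the only output. Section 8.1.2.1 tabulates PK parameters by dose regimen, and a fit with continuous dose would produce a slope. Neither sets a criterion, and 8.1.2.2 does not ask for the slope or its interval to be reported. The two SAPs cover efficacy and safety, so their silence on PK shows nothing.

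The stakes are modest. The RPTD rule in 6.1.8.7 does not use a proportionality finding, no passage says that non-significance will be read as proportionality, and Protocol 3.0 already reports proportional steady-state AUC from 150 to 800 mg in CLL. That lowers the importance of the analysis. It does not make a non-significant test in AML with cytarabine evidence of proportionality.

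**Conclusion.** The point holds as a minor one. Inference on dose proportionality rests on a trend test alone, kept after the study had given only 600 and 800 mg, with 10 subjects at the higher dose. A non-significant result cannot be taken as support for proportionality. Flat exposure is more likely missed than found if the CV exceeds about 27-34%, assuming 6-12 v 10 subjects and two-sided 0.05. Half-proportional exposure would more likely be missed than found even at CV 20% on those numbers.

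A reader might go further and conclude that the study can neither support nor exclude proportionality. That prejudges the data: with a low enough CV the interval would exclude flat exposure, as the CV 30% example shows.

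**What to change.** In section 8.1.2.2, replace the trend-test sentence with an estimate: the ratio of dose-normalized Cmax and AUC at 800 v 600 mg (or the power-model exponent), with a 90% CI from the same model, in line with the cytarabine interaction analysis. Add that a non-significant dose effect will not by itself be taken as evidence of proportionality. Do not write the conclusion in advance; let the interval show what is excluded.

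The cost is a change of wording and one more estimate from a model already planned, with no new data. If the analysis has already been run, the change can be made in reporting. The downside is that the interval will probably be wide, so a positive claim of proportionality may not be possible from this study.

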8.1.2.3 Missing Values and Model Violations

All available data will be included the mixed effect analyses. Data exclusion, if any, will be documented and justification provided.

Normally distributed values of PK variables (C_{max} , AUC, etc.) will be determined without replacing missing individual concentration values, simply using the available data, and if necessary doing the analysis with some missing values for a PK variable. However, if a missing individual concentration results in a value of a PK parameter that may be too low or too high to a meaningful degree, the value of the PK parameter will tentatively be considered missing. In this case, a value for the missing individual concentration may be imputed so that an appropriate value of the PK parameter can be included in the analysis. The imputed value will be obtained using appropriate methodology that takes into account the individual characteristics of the subject.

If an outlier is identified and/or a pronounced non-normal probability distribution is observed (after logarithmic transformation for C_{max} and AUC), then a non-parametric analysis may also be performed. Such a model violation may be identified by graphical methods, measures of non-normality (e.g., skewness, kurtosis) or other appropriate methods. If the regimens have unequal variances to the extent that conclusions might be affected, then approximate methods that allow for unequal variances will be used.

8.1.3 Efficacy Summaries

Efficacy will include analyses of ORR as defined by CR + CRi + PR, CR rate, CRi rate, CRh rate, CR + CRi rate, CR + CRh rate, DOR, EFS, OS, the exploratory analysis of the proportion of for all subjects who achieve MRD negativity, the proportion of subjects who are transfusion independent post baseline, and the proportion of subjects who undergo subsequent stem cell transplant. Transfusion support needs will be recorded to define ongoing transfusion dependence.

8.1.3.1.1 Overall Response Rates

CRh (Complete remission with partial hematologic recovery) is a derived response based on bone marrow blast count and hematology lab values. A response of CRh is achieved when the following criteria are met:

- Bone marrow with < 5% blasts and
- peripheral blood neutrophil count of $\geq 0.5 \times 10^3/\mu\text{L}^*$ and
- peripheral blood platelet count $\geq 0.5 \times 10^5/\mu\text{L}^*$

*For a bone marrow sample collected before the last cycle of study treatment, the hematology lab results collected from the date of bone marrow sample collection up to Day 1 of a subsequent cycle of study treatment will be used for CRh analysis. For a bone marrow sample collected during or after the last cycle of study treatment, the hematology lab results collected within 14 days after bone marrow sample collection date will be used for CRh analysis.

CR + CRh rate will be defined as the proportion of subjects who achieve CR or CRh at any time point during the study. Subjects who never achieve CR or CRh or have not had IWG disease assessment will be considered to be non-responders in the calculation of CR + CRh rate.

Overall response rate will be defined as the proportion of subjects who achieve a CR, CRi, or PR at any time point during the study per the IWG criteria for AML. Subjects who do not achieve a response of CR, CRi, or PR will be considered to be non-responders participating in the calculation of the ORR rate.

In addition, the proportion of subjects who achieve CR, the proportion of subjects who achieve a CRi, the proportion of subjects who achieve a CRh, and the proportion of subjects who achieve CR + CRi will be summarized. The 95% confidence interval based on the binomial distribution will be provided for CR + CRh rate, ORR, CR rate, CRi rate, CRh rate, and CR + CRi rate.

8.1.3.1.2 Duration of Response

Duration of response will be defined as the number of days from the date of first response (CR, CRi, or PR) per the IWG criteria for AML to the earliest recurrence or PD. If a subject is still responding, then the subject's data will be censored at the date of the subject's last available disease assessment. For subjects who never experience response, the subject's data will not be included unless otherwise indicated. Duration of response will be analyzed by Kaplan-Meier methodology using data for all enrolled subjects who responded. Median DOR will be calculated and the corresponding 95% confidence interval will be presented.

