4.0 Study Objective

The primary objectives of the Phase 1 portion are to assess the safety profile, characterize PK, determine the dose schedule, the maximum tolerated dose (MTD), and the recommended Phase 2 dose (RPTD) of venetoclax (ABT-199/GDC-0199) in combination with LDC in treatment-naïve subjects with AML who are ≥ 65 years of age and who are not eligible for standard induction therapy due to co-morbidity or other factors.

The primary objectives of the initial Phase 2 portion of the study are to evaluate the preliminary estimates of efficacy including the overall response rate (ORR), and to characterize the toxicities of the combination at the RPTD.

The primary objective of Phase 2 Cohort C is to evaluate the ORR for subjects allowed additional supportive medications (strong CYP3A inhibitors) if medically indicated.

The secondary objectives of the initial Phase 2 portion and Phase 2 Cohort C are to evaluate leukemia response (rates of CR, CRi, PR, and MLFS), duration of response (DOR) and overall survival (OS).

Additional exploratory objectives of both phases of the study may be evaluated to find biomarkers that may serve as surrogates or predictors for clinical outcomes in future studies of venetoclax in AML.

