5.3.3 Efficacy Variables

Efficacy Assessments

Responses will be evaluated based on the revised guidelines by the International Working Group (IWG) for AML.³⁸ As a significant number of the subjects in this study might have antecedent hematologic illnesses, hematologic response will also be evaluated. Transfusion dependence is defined as having received ≥ 2 units of RBCs and or platelets

within 8 weeks prior to study treatment. Duration of Response will be measured from the time when all response criteria are first met until recurrent or progressive disease is documented.

Criteria for Evaluation is as follows:

- CR: Absolute neutrophil count $\geq 10^3/\mu\text{L}$, platelets $\geq 10^5/\mu\text{L}$, red cell transfusion independence, and bone marrow with $< 5\%$ blasts.
- CRi: bone marrow with $< 5\%$ blasts, and peripheral neutrophils of $< 10^3/\mu\text{L}$ or platelets $< 10^5/\mu\text{L}$.
- PR: all of the hematologic values for a CR but with a decrease of at least 50% in the percentage of blasts to 5% to 25% in the bone marrow aspirate.
- MLFS: less than 5% blasts in an aspirate and/or bone marrow core sample. There should be no blasts with Auer rods or persistence of extramedullary disease. The presence of a unique phenotype (by flow cytometry) identical to what was found in the pretreatment specimen (e.g., CD34, CD7 coexpression) should be viewed as persistence of leukemia.
- RD: failure to achieve CR, CRi, PR; only including subjects surviving at least 7 days following completion of initial treatment cycle, with evidence of persistent leukemia by blood and/or bone marrow examination.
- PD: one or more of the following: $\geq 50\%$ decrement from maximum response levels in neutrophils or platelets, a reduction in hemoglobin by at least 2 g/dL, or transfusion dependence,* not due to other toxicities and bone marrow blast $\geq 5\%$.

In addition to the response determination using the above IWG AML response criteria, each subject will also be evaluated for hematologic response and complete remission with partial hematologic recovery (CRh).

- HR: improvement in peripheral blood counts with all of the following: fewer absolute peripheral blood blasts than prior to initiating study treatment for subjects presenting with peripheral blood blasts, ANC ≥ 500 (cells/ μL),

platelets $\geq 0.25 \times 10^5$ (platelets/ μL), and no more than 2 units of packed red blood cells within a 28-day period.

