8.1.3.1.3 Event-Free Survival

Event-free survival (EFS) will be defined as the number of days from the date of first dose to the date of earliest evidence of progression or relapse, subsequent treatment other than stem cell transplant while in composite complete response (CR + CRi), or death. If the specified event (relapse, start of subsequent treatment, or death) does not occur, patients will be censored at the date of last disease assessment. Data for subjects without any disease assessments performed after the baseline visit will be censored at the date of first dose plus 1 day. Event-free survival (EFS) will be analyzed by Kaplan-Meier methodology. Median EFS will be calculated and 95% confidence interval for median EFS will be presented.

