6.2 Planned Efficacy Analyses for Each Analysis Dataset

A list of contents of efficacy analyses described in the Statistical Methods section (Section 8.0) is provided below. The list of analyses will be performed for all three analysis datasets separately. Data will not be pooled across studies.

- Complete remission (CR) rate (Analysis datasets 1 - 3)
- Complete remission with partial hematologic recovery (CRh) rate (Analysis datasets 1 - 3)
- CR + CRh rate (Analysis datasets 1 - 3)
- CR + CRh rate by the initiation of Cycle 2 (Analysis datasets 1 - 3)
- Time to the first response of CR + CRh (Analysis datasets 1 - 3)
- Time to best response of CR + CRh (Analysis datasets 1 - 3)
- Duration of CR (Analysis datasets 2 - 3)
- Duration of CR + CRh (Analysis datasets 1 - 3)
- CR + CRi rate (Analysis datasets 2 - 3)
- CR + CRi rate by the initiation of Cycle 2 (Analysis datasets 2 - 3)
- Time to the first response of CR + CRi (Analysis datasets 2 - 3)
- Time to best response of CR + CRi (Analysis datasets 2 - 3)
- Duration of CRi (Analysis datasets 2 - 3)
- Duration of CR + CRi (Analysis datasets 2 - 3)
- Objective Response Rate (CR + CRi + PR) (Analysis datasets 2 - 3)
- Overall survival (OS) (Analysis datasets 2 - 3)

- Post baseline RBC/Platelet transfusion independence and duration of post baseline RBC/Platelet transfusion independence (Analysis datasets 1 - 3)
- Time to first RBC/platelet transfusion (Analysis datasets 2 - 3)
- Time to the first recurrent RBC/platelet transfusion (Analysis dataset 2 - 3)
- Time to first Grade 3 or above TEAE hemorrhage event (SMQ narrow) (Analysis datasets 2 - 3)
- Time to first Grade 3 or above TEAE SOC of "infections and infestations" event (Analysis datasets 2 - 3)
- Time to first hospitalization due to SAE (Analysis datasets 2 - 3)

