8.1.5 Duration of CR

Duration of CR is defined as number of days from date that subject achieved CR to the first date of relapse, clinical disease progression or death due to disease progression, whichever occurred earliest. If a subject is still responding at the data cutoff date, then the subject's data will be censored. The disease assessment data after the onset of any post-treatment therapy will not be included in the duration of CR analysis. The detailed censoring rule is described in [Table 4](#). For each analysis dataset, the distribution of duration of CR will be estimated using Kaplan-Meier methodology. Median duration of CR with the corresponding 95% CI will be provided from Kaplan-Meier estimation.

Table 4. Event/Censor and Corresponding Event/Censor Time for Duration of CR or CR + CRh

Situation	Event/Censor	Event Time/Censor Time
IWG disease progression (PD) or Clinical disease progression (CPD) on or prior to any post-treatment therapy and data cutoff date, whichever is earliest	Event	Earliest PD date
Death due to disease progression on or prior to data cutoff date regardless whether it occurred after any new post-treatment	Event	Death date
Neither PD nor CPD nor Death due to disease progression and without post-treatment therapy on or prior to the data cutoff date	Censor	Last disease assessment date (bone marrow or hematology lab collection date) on or prior to the data cutoff date
Neither PD nor CPD nor Death due to disease progression but having post-treatment therapy on or prior to the data cutoff date	Censor	Start of post-treatment therapy

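### Protocol duration of response does not count death from AML as an event, which leaves it censored by default, and the SAP has no duration analysis for CR + CRi + PR

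*Protocol*

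**What the plan says.** **Protocol.** Section 4.0 lists "duration of response (DOR) and overall survival (OS") among the secondary objectives of the initial Phase 2 portion and Cohort C. Section 8.1.3.1.2 starts DOR at the first CR, CRi or PR and ends it "per the IWG criteria for AML to the earliest recurrence or PD". Section 5.3.3 agrees: the clock runs "until recurrent or progressive disease is documented". The one censoring sentence is: "If a subject is still responding, then the subject's data will be censored at the date of the subject's last available disease assessment". The PD criteria in 5.3.3 combine worsening counts, hemoglobin or transfusion need, "not due to other toxicities and bone marrow blast" of at least 5%; death is not among them. The next subsection, on event-free survival, does name death: its events include "subsequent treatment other than stem cell transplant while in composite complete response (CR + CRi), or death".

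**Efficacy SAP.** Sections 8.1.5 and 8.1.6 end the durations of CR and of CR + CRh at relapse, clinical progression or death from progression. Table 4 classes the following as an event on the death date: "Death due to disease progression on or prior to data cutoff date regardless whether it occurred after any new post-treatment". A subject with none of these events who starts new therapy is censored at its start. Section 6.2 lists the rate of CR + CRi + PR but no duration for that group. It does list duration of CRi and "Duration of CR + CRi (Analysis datasets 2 - 3"), but Section 8.1 has no definition or event and censoring table for either. The duration-of-response sensitivity analyses in 8.1.11 cover CR + CRh, CRh and CR only.

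**The concern.** With recurrence and PD as the only events, a responder who dies of AML before progression is documented has no event date. A Kaplan-Meier program then treats the subject as censored. That censoring is informative, because the subject leaves the risk set by failing from the disease. The curve then estimates time to documented recurrence as if AML death did not end a response, and it lies above the curve that most readers would take DOR to mean.

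The SAP would normally settle such a point, but it has no analysis of DOR for CR + CRi + PR. The rule it does contain belongs to other durations. An analyst would have to choose the handling of these deaths after the data are known. A protocol DOR reported beside the SAP durations would also end at a different set of events.

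**Working it through.** The plan states no figure for DOR, so there is nothing to reproduce. The check compares the texts and then gives a scale under stated assumptions.

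**1. The rules side by side**

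| Situation | Protocol DOR (CR, CRi or PR) | SAP Table 4 (CR; CR + CRh) |
|---|---|---|
| Documented recurrence or PD | Event | Event, if on or before new therapy |
| Clinical progression | Not named separately | Event, if on or before new therapy |
| AML death, no documented PD | No rule; not in the event list | Event on the death date, even after new therapy |
| Death from another cause | No rule | Not an event |
| New therapy, no event | No rule | Censored at its start |
| Still responding | Censored at last disease assessment | Censored at last disease assessment |

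Durations of CRi and CR + CRi have no column because no rule is written for them.

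**2. Can the case arise?** Yes. Under Protocol 5.3.1.1, routine response marrows stop after two successive CRs and are repeated if there is clinical evidence of recurrence. Table 3 marks no marrow at the 12-week post-treatment visits. A responder can therefore die of AML before a marrow meets the PD criteria.

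**3. Scale (illustration only)**

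Assumed inputs, none from the documents:
- exponential times with a disease-failure hazard h = 0.06 per month;
- a share s of failures that are AML deaths without prior documented PD, drawn at random from all failures;
- other-cause deaths censored under both rules.

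Formulas:
- AML death as an event: median = ln 2 / h; 12-month estimate = exp(−12h).
- AML death censored at death: the hazard seen by Kaplan-Meier is h(1 − s), so median = ln 2 / [h(1 − s)] and 12-month estimate = exp(−12h(1 − s)).

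Results:

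| Rule | Median (months) | 12-month estimate |
|---|---|---|
| AML death an event | 0.6931/0.06 = 11.55 | exp(−0.72) = 48.7% |
| Censored, s = 10% | 0.6931/0.054 = 12.8 | exp(−0.648) = 52.3% |
| Censored, s = 20% | 0.6931/0.048 = 14.4 | exp(−0.576) = 56.2% |
| Censored, s = 30% | 0.6931/0.042 = 16.5 | exp(−0.504) = 60.4% |

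Censoring at the last assessment on a 12-week grid, by simulation, gives slightly smaller medians: 12.7, 14.2 and 16.1 months.

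**4. What drives the size.** The ratio of medians is 1/(1 − s), whatever the hazard: 1.11, 1.25 and 1.43 for 10%, 20% and 30%. With an assumed median of 8 months, the same shares give 8/0.9 = 8.9, 8/0.8 = 10.0 and 8/0.7 = 11.4 months.

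**5. Against sampling error.** Assume 40 responders and no censoring before 12 months. The standard error of the 12-month estimate is √(0.487 × 0.513/40) = 0.079, or 7.9 points. The gaps of 3.6, 7.5 and 11.7 points are about 0.5, 1.0 and 1.5 standard errors.

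**The case against.** Several points on the other side stand.

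- **The protocol does not say that AML deaths are censored.** A reader might infer an explicit rule, but the censoring sentence covers only subjects still responding, and a subject dead of AML is not plainly one of them. An analyst could date the death as recurrence. The protocol is silent on the point; censoring is what follows when its event list is applied literally.
- **The two documents do not define one endpoint in two opposite ways.** Table 4 governs CR and CR + CRh. Protocol DOR covers CR, CRi or PR. The responder sets differ whatever is done with deaths.
- **DOR is not without any planned analysis.** Protocol 8.1.3.1.2 itself specifies Kaplan-Meier, the median and a 95% confidence interval among responders. The gap is in the SAP. The SAP also does not ignore CR + CRi: 8.1.12 plans a Kaplan-Meier median by MRD for it, but without an event and censoring rule.
- **The documents do not show that such deaths are likely.** Marrow is repeated on clinical suspicion and scheduled at the Final Visit, clinical progression is assessed at least every 3 cycles, and post-treatment visits include hematology and disease assessment. No frequency is given.
- **Nor do they show that the fastest-failing responders are the ones lost.** The illustration removes a random share of failures.
- **The consequence is limited.** Deaths of any cause count in event-free survival and overall survival, and SAP 9.0 plans no formal testing.

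These points bound the size and correct the wording. They do not supply the missing rule.

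**Conclusion.** The point holds in a limited form. Protocol DOR names only recurrence and PD as events and has no rule for a responder who dies. An AML death without documented PD is censored by default, and that censoring can only lengthen DOR. The SAP applies a different rule to related durations, has none for CRi and CR + CRi, and has no duration analysis for CR + CRi + PR.

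The direction of the bias is clear wherever these deaths are censored. Its size is not known. The 11% to 43% longer median for shares of 10% to 30% rests wholly on the assumed share and exponential times; the values in months also rest on the assumed hazard. For a descriptive secondary endpoint in a non-randomized study this should be corrected, but it does not threaten the primary response-rate analysis.

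**What to change.** **Protocol 8.1.3.1.2 and 5.3.3.** Count death due to disease progression as a DOR event on the date of death. State separately how death from another cause is handled and what happens when new therapy starts. Copying Table 4 without comment is not enough: it counts an AML death even after new therapy but censors at the start of new therapy when no event follows. The protocol should adopt or change that combination explicitly.

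**Efficacy SAP 6.2, 8.1 and Table 4.** Add DOR for CR + CRi + PR and extend the Table 4 rules to the durations of CRi and CR + CRi. Alternatively, state that the protocol DOR is replaced, and by which duration.

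**Cost.** Wording in two documents and one more Kaplan-Meier output. Date and cause of death are already planned data items (Protocol 5.3.1.1 and 6.1.3.1). Reported DOR would be somewhat shorter than under default censoring.
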